9.3. Additional Outcomes and Analyses

Additional outcomes of interest include the effects of the GAD-Alum vaccine on antigen specific immune activity which will be assessed from blood draws as outlined in the Schedule of Assessments (Appendix 1). The specimens will allow an assessment of whether reactivity can be found for autoantigen-specific peptides. Proliferation, cytokine production, and other methodologies will measure immune responses. T cell lines and clones may be made from antigen-reactive individuals.

Additional analyses will compare the results in this trial to other trials using GAD-alum vaccine and other TrialNet studies. Data in this trial will be used in conjunction with other TrialNet data for exploratory analysis.

Additional analysis will be conducted evaluating primary, secondary, and other outcomes using the subjects that have received their intended treatment ("per-protocol analysis).

9.4. Sample Size and Power Calculations

The primary analysis will compare the difference between each treated group separately versus the placebo group (two pair-wise comparisons) in the levels of $\log(Y_{Cp} + 1)$ using an ANCOVA model adjusting for gender, baseline age, and baseline $\log(Y_{Cp} + 1)$. Estimates of the mean and standard deviation of $\log(Y_{Cp} + 1)$ (expressed algebraically as: $\hat{\mu}_{\log(Y_{Cp}+1)}$ and $\hat{\sigma}_{\log(Y_{Cp}+1)}$) in the placebo group were obtained from prior studies. Among patients with baseline C-peptide > 0.2 pmol/ml and \geqq gd2 years, $\hat{\mu}_{\log(Y_{Cp}+1)} = 0.248$ and $\hat{\sigma}_{\log(Y_{Cp}+1)} = 0.179$ (3). An approximation of the mean of Y_{Cp} for the placebo group is calculated by applying the inverse transformation; this yields 0.282 pmo/mL.

Using standard equations for the comparison of two means, a sample size of 38 patients with complete data needed for the primary analysis per group, would provide power of 85% to detect a 60% increase (on the original scale) in the geometric mean C-peptide with either treatment relative to the placebo group using a test at the 0.025 level (one-sided).

Assuming that 10% of the patients will be "lost" (unavailable for the primary analysis), this study will require enrolling 42 eligible patients per group (126 total). The plan is to follow these patients two years from baseline and for up to 2 additional years post-treatment if residual beta-cell function or immunological effects are detected.

TrialNet: GAD Intervention Protocol

The exact final sample size can not be fixed to be exactly because of staggered patient entry. The study will be closed to new patients entering the screening phase when the total number then randomized plus a fraction of those in screening is expected to provide the proper number of eligible patients. Patients who had already conducted the initial screening visit at that time will be allowed to complete screening and be randomized if both consenting and eligible.

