9.1. Primary Outcome and Analyses

The primary outcome of each participant is the area under the stimulated C-peptide curve (AUC) over the first 2 hours of a mixed meal glucose tolerance test conducted at the one-year visit. The AUC is computed using the trapezoidal rule that is a weighted sum of the C-peptide values over the 120 minutes. The weighted mean C-peptide is simply AUC/120 (pmol/mL). Let $Y_{Cp}^{GAD\times3}$, $Y_{Cp}^{GAD\times2}$, and $Y_{Cp}^{Control}$ represent the mean C-peptide value for study patients receiving three injections with 20µg GAD-Alum, those receiving two injections with 20µg GAD-Alum and those receiving placebo, respectively. Likewise, let $\mu_{Cp}^{GAD\times3}$, $\mu_{Cp}^{GAD\times2}$, and $\mu_{Cp}^{Control}$ represent the mean of Y_{Cp} for these groups, respectively.

The primary statistical hypotheses to be assessed in the study are:

$$H_{0}: \mu_{Cp}^{GAD\times3} = \mu_{Cp}^{Control} \text{ versus } H_{a}: \ \mu_{Cp}^{GAD\times3} > \mu_{Cp}^{Control}$$
$$H_{0}: \mu_{Cp}^{GAD\times2} = \mu_{Cp}^{Control} \text{ versus } H_{a}: \ \mu_{Cp}^{GAD\times2} > \mu_{Cp}^{Control}$$

The primary analysis will be conducted on the transformed Y_{Cp} using the log function: $\log(Y_{Cp} + 1)$. This provides better normal distributional behavior by the test statistic. The comparison between any two treatment arms will be based on a t-test of treatment effect in an ANCOVA model adjusting for gender, baseline age, and baseline $\log(Y_{Cp} + 1)$ (49).

The Holm closed-sequential procedure for multiple tests (46) will be used to control the type I error probability to not exceed 0.05, one-sided, for the set of two pairwise group comparisons.

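### Section 9.4 attaches its 85% power to a 60% rise in the geometric mean of C-peptide, but the figure was computed for a 60% rise in exp(mean log(Y+1)) − 1, which is a different quantity

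*Protocol*

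**What the plan says.** Section 9.1 defines Y as the weighted mean C-peptide (AUC/120) at one year and writes the hypotheses on group means. On the test itself it says "The primary analysis will be conducted on the transformed" outcome, log(Y+1), using ANCOVA with gender, baseline age and baseline log(Y+1). Holm's procedure is used "to control the type I error probability to not exceed 0.05, one-sided, for the set of two pairwise group comparisons".

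Section 9.4 takes a placebo mean of 0.248 and an SD of 0.179 for log(Y+1) from prior studies. It says that an approximate placebo mean of Y "is calculated by applying the inverse transformation; this yields 0.282 pmo/mL". It then asks for "a sample size of 38 patients with complete data needed for the primary analysis per group". By its account this number "would provide power of 85% to detect a 60% increase (on the original scale) in the geometric mean C-peptide with either treatment". Each active arm is compared with placebo, and the level for each test is set at 0.025, one-sided. The section reports no mean or SD of log(Y) and no distribution of Y.

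**The concern.** The geometric mean of C-peptide is exp(mean log Y). Back-transforming a mean of log(Y+1) gives the geometric mean of (Y+1), minus 1. When Y is large compared with 1 the two nearly agree. Here Y is around 0.28 pmol/mL, so the added 1 dominates and they differ visibly. Section 9.4 calls the back-transformed value an approximate mean of Y and then states the detectable effect as a change in the geometric mean.

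This is the protocol's only statement of what effect the trial is powered to detect. Anyone comparing the result, or another trial's effect size, with a 60% rise in geometric mean C-peptide would attach 85% power to an effect for which it was not calculated.

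**Working it through.** **Inputs from the protocol.** Placebo mean of log(Y+1) 0.248, SD 0.179, n = 38 per group, one-sided 0.025 (all 9.4). The 0.025 is the first Holm step of the one-sided 0.05 in 9.1.

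**Reproducing the 85%.**
- Back-transformed placebo value: exp(0.248) − 1 = 0.2815, printed as 0.282.
- Raised by 60%: 1.6 × 0.2815 = 0.4503.
- Difference in mean log(Y+1): log(1.4503) − 0.248 = 0.1238.
- SE = 0.179 × √(2/38) = 0.0411, so z = 0.1238/0.0411 = 3.01.
- Power = Φ(3.01 − 1.96) = 85.4%. Solving for 85% power returns n = 38.

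One-sided 0.05 gives 91.5% and n = 31, and a shift of log 1.6 gives nearly 100%. Neither matches, so the 60% was applied to exp(mean log(Y+1)) − 1.

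**Direction, without a distribution.** Let u = log(Y+1), with Y positive and not constant.
- exp(E u) − 1 always exceeds exp(E log Y), so 0.282 is not the placebo geometric mean.
- If every Y is multiplied by 1.6, u becomes log(1.6eᵘ − 0.6). This is concave in u, so the mean difference is below 0.1238. Its slope exceeds 1, so the treated SD is above 0.179. Both lower the power.
- If u is shifted by a constant d, the log-ratio log[(eᵘ⁺ᵈ − 1)/(eᵘ − 1)] is convex in u. A shift of 0.1238 therefore raises the true geometric mean by more than 60%, and the shift that gives exactly 60% is smaller than 0.1238.

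**Size, with assumed distributions.** Six two-parameter families were each matched to mean 0.248 and SD 0.179 of log(Y+1). Each row gives the power for a 60% rise in the true geometric mean, at n = 38 and one-sided 0.025, unadjusted.

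| Assumed placebo distribution | True geometric mean | Y × 1.6, SD 0.179 in both arms | Y × 1.6, treated SD as implied | Constant shift (size), SD 0.179 |
|---|---|---|---|---|
| Truncated normal on log(Y+1) | 0.193 | 80% | 64% | 35% (0.064) |
| Weibull Y | 0.198 | 80% | 64% | 39% (0.069) |
| Gamma Y | 0.202 | 80% | 64% | 42% (0.072) |
| Gamma on log(Y+1) | 0.213 | 80% | 65% | 50% (0.080) |
| Lognormal Y | 0.222 | 80% | 66% | 57% (0.088) |
| Lognormal on log(Y+1) | 0.229 | 81% | 67% | 61% (0.092) |

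Under multiplication by 1.6 the difference is 0.115–0.116, so for example Φ(0.115/0.0411 − 1.96) ≈ 80%. The implied treated SD is 0.24–0.25. In the first row the SE becomes √((0.179² + 0.248²)/38) = 0.0496, and Φ(0.115/0.0496 − 1.96) ≈ 64%.

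**What the planned 0.1238 means for the true geometric mean.** As a constant shift it is about a 1.8- to 2.1-fold rise. As a proportional effect it is about a 1.65-fold rise, close to the stated 1.6.

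**The case against.** The strongest reply is that this is a loose label on a consistent calculation. The inverse transformation and its result stand just before the power sentence, and 0.282 is the only original-scale placebo value given. A careful reader would apply the 60% to it and recover 85%. This stands: the arithmetic is right for the quantity used, and the fault lies in the name. The name still denotes a different, well-defined quantity, so the sentence is wrong as printed.

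A second reply concerns size. An increase on the original scale is naturally read as proportional. With the protocol's single SD, power is then about 80%, and 85% corresponds to about a 65% rise. This also stands. A reader might infer that the same formula gives only 39–66%, but that leaves out the 80% case, and figures in the mid-60s need a larger treated-arm SD than the protocol uses. A reader might also infer that the planned difference is far more than a 60% rise; that holds only for a constant shift.

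A third reply is that ANCOVA recovers power. At an assumed R² of 0.3, the proportional case with common SD reaches about 92%. The protocol states no R² and takes no such credit in 9.4. The same credit would lift its own 85% to about 95% (z = 3.01/√0.7 = 3.60), so the ordering is unchanged.

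Finally, writing the hypotheses on means of Y and testing log(Y+1) is stated openly in 9.1 and is not a contradiction.

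**Conclusion.** The point holds and is modest in size. The 85% belongs to a 0.124 difference in mean log(Y+1), equivalently 0.282 to 0.450 pmol/mL on the back-transformed scale, and not to a 60% rise in the geometric mean of C-peptide. For the effect as worded, the unadjusted formula gives less than 85% under both effect models examined, and that direction needs no distribution of Y.

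The amount does need one. It is about 80% for a proportional effect with the SD held at 0.179, about 64–67% if the treated SD grows as that effect implies, and about 35–61% for a constant shift. The low end is sensitive to values of Y near zero, on which the protocol gives no information.

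A reader might infer that the trial is too small or the sample size miscalculated. The protocol does not support that: n = 38 is right for the effect actually used.

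**What to change.** In 9.4, replace the description of the detectable effect as a rise in geometric mean C-peptide with: *a difference of 0.124 in mean log(Y+1), i.e. a 60% increase in the back-transformed mean exp(mean log(Y+1)) − 1, from 0.282 to 0.450 pmol/mL*.

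If a claim about the geometric mean of C-peptide is kept, give its lower power as a range, with the assumed distribution of Y, the effect model and any credit for covariate adjustment stated.

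The cost is one sentence. Sample size, test and alpha are unchanged; the stated detectable effect becomes less familiar to read, but it is the one that was computed.

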9.5. Interim Monitoring Plan

Interim analyses will be conducted periodically during the study and will be reviewed by the TrialNet DSMB for assessment of effectiveness and safety. The Lan-DeMets spending function with an O'Brien-Fleming boundary will be used to protect the type I error probability (47) and to assess the significance of the interim results that emerge during the trial. The spending function that approximates the O'Brien-Fleming boundaries is:

$$\alpha_1(t^*) = 2 - 2\Phi\left[\frac{Z_{\alpha/2}}{\sqrt{t^*}}\right]$$

where t^* is the information fraction ($0 < t^* \le 1$), α_1 is the α -*level* of the interim (onesided) test and α is the over-all type I error.

The monitoring plan will allow for early termination based on the treatment effects on Cpeptide values at 1 year of follow-up. The DSMB will also consider early termination due to absence of a treatment effect (i.e. futility) based on the method suggested by Ellenberg et al (49). The stopping rule is: if the t-test (as described in the primary analysis and positive values reflect a higher Y_{CP} values among the experimental group) is

less than or equal to 0 at $t^* \ge 0.5$, the study should be stopped based on the futility of rejecting the null hypothesis at the full completion of the trial. Additional analysis will assess potential adverse outcomes of treatment and will assess the incidence of all severe adverse events.

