11.1.5. Data and Safety Monitoring Board (DSMB)

The DSMB will meet approximately every 6 months to review efficacy issues and adverse events prepared by the Coordinating Center. All adverse events will be recorded on the adverse event forms, which will be sent to the local IRBs, per their reporting requirements, and to the Coordinating Center. The DSMB will independently evaluate whether the adverse events constitute grounds to discontinue the study.

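### Section 9.5 defines the cumulative spending function as the level of each interim test and does not say which alpha each of the two comparisons spends

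*Protocol*

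**What the plan says.** Section 9.5 (Interim Monitoring Plan) provides for periodic interim analyses, reviewed by the DSMB for effectiveness and safety, and allows early termination on the one-year C-peptide effect. It names the Lan-DeMets spending function with an O'Brien-Fleming boundary and prints α₁(t*) = 2 − 2Φ(Z_{α/2}/√t*). It then explains the symbols: α₁ is the level of the "interim (onesided) test and α is the over-all type I error".

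Section 9.1 (Primary Outcome and Analyses) has two primary comparisons, each GAD-alum arm against placebo. It states that "The Holm closed-sequential procedure for multiple tests (46) will be used" and that the aim is "to control the type I error probability to not exceed 0.05, one-sided, for the set of two pairwise group comparisons". Section 9.4 (Sample Size and Power Calculations) sizes each comparison at one-sided 0.025.

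On frequency, section 11.1.5 says "The DSMB will meet approximately every 6 months to review efficacy issues and adverse events". No section gives a number of formal efficacy analyses or their information fractions.

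**The concern.** The printed formula is right, but the definition attached to it is not. A spending function gives the total error used up to t*. Boundaries after the first look are solved from the increments and from the correlation between looks. If the function value is used as the level of each test, the last test (t* = 1) runs at full α, as if nothing had been spent earlier.

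The second difficulty is which α enters the function. Section 9.5 says the overall error, and the only overall error in the protocol is the 0.05 that section 9.1 sets for the pair of comparisons. Section 9.5 does not mention the pair or Holm, and section 9.1 does not mention error spent at interim looks. A DSMB following section 9.5 to the letter could test each comparison at interim levels derived from 0.05 and then apply Holm at the end as if no looks had taken place. An efficacy stop or final claim made that way could carry a family-wise error above the stated 0.05.

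**Working it through.** **Inputs.** Section 9.1: family-wise error 0.05 one-sided; Holm on two comparisons (0.025 at the first step, then 0.05). Section 9.4: placebo mean of log(Y+1) 0.248, SD 0.179, 60% increase on the original scale, 38 evaluable per group, one-sided 0.025, power 85%. Section 4.5: three equal arms, so the two comparisons share a placebo group and their test statistics correlate at 0.5. Section 9.5: the function above. **Assumption:** 2 to 5 equally spaced analyses, counting the final one.

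**Step 1. Reproduce the plan's own figure.**
- Placebo mean: exp(0.248) − 1 = 0.281 (the plan gives 0.282). A 60% increase gives 1.6 × 0.281 = 0.450.
- Difference on the log scale: log(1.450) − 0.248 = 0.1238.
- Standard error: 0.179 × √(2/38) = 0.0411. Standardised effect: 0.1238/0.0411 = 3.015.
- Power at one-sided 0.025: Φ(3.015 − 1.960) = 85.4%.

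The stated 38 per group and 85% are reproduced. At one-sided 0.05 only 31 per group would be needed, so the sizing does use the first Holm level for each comparison.

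**Step 2. Values of the function.** For example, with α = 0.05 and t* = 0.5: 2 − 2Φ(1.960/√0.5) = 2 − 2Φ(2.772) = 0.0056.

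| α entered | t* = 0.5 | t* = 0.75 | t* = 1 |
|---|---|---|---|
| 0.05 | 0.0056 | 0.0236 | 0.05 |
| 0.025 | 0.0015 | 0.0096 | 0.025 |

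The function returns the whole of α at t* = 1, which shows that it is cumulative. With α = 0.025 and looks at t* = 0.5 and 1, the increments are 0.0015 and 0.025 − 0.0015 = 0.0235. The boundaries solved from them have nominal levels of 0.0015 and 0.0244, not 0.0015 and 0.025.

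**Step 3. Family-wise error when neither arm works.** Pairs of Brownian paths with correlation 0.5 were simulated 4 million times per schedule; results vary by about 0.1 point between runs. In the first two result columns the function value is used as the level of each interim test, and the final analysis is Holm without adjustment (first step 0.025). In the last column the boundaries are solved from cumulative spending.

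| Analyses | Literal interim levels, α = 0.05 each | Literal interim levels, α = 0.025 each | Cumulative boundaries, α = 0.025 each |
|---|---|---|---|
| 2 | 5.0% | 4.6% | 4.5% |
| 3 | 5.9% | 4.9% | 4.5% |
| 4 | 6.7% | 5.0% | 4.5% |
| 5 | 7.3% | 5.2% | 4.5% |

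Moving from the first result column to the second changes only α and removes 0.4 to 2.1 points. Moving from the second to the third corrects only the definition and removes 0.1 to 0.7 points.

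**Step 4. Cost of the correct boundaries.** With four analyses and α = 0.025, the critical values are z = 4.33, 2.96, 2.36 and 2.01. Counting only the final look, power is Φ(3.015 − 2.01), about 84%. Adding the chance of crossing earlier, by multivariate normal integration, gives about 84.8%.

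**The case against.** The strongest reply is that section 9.5 names and cites Lan-DeMets, calls the formula a spending function, prints it correctly and says that its purpose is to protect the type I error. A statistician applying that method would solve the boundaries from cumulative spending whatever the loose sentence says. Section 9.1 fixes Holm and section 9.4 uses 0.025, so a careful reader can arrive at a valid rule. How Holm combines with group-sequential boundaries is often left to an SAP or a DSMB charter.

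Much of this stands. It rules out the flat statement that the family-wise error is not protected, because the named methods do control it when combined properly. It also rules out the larger figures that a reader might infer. Spending the full 0.05 on each comparison at every look including the last would give about 9% to 10% under the literal levels, and about 8.7% with correct cumulative boundaries. No section gives 0.05 to each comparison at the final analysis, and the Holm rule in section 9.1 excludes it. Nor does the six-monthly DSMB meeting in section 11.1.5 establish four formal boundary tests, since the protocol does not say that each meeting carries one.

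The reply does not dispose of the definition. That is a rule stated wrongly in the protocol, not a detail deferred to another document. The α named beside it is the overall error, which does not match the 0.025 used for sizing.

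**Conclusion.** The point holds in a limited form. Section 9.5 misdefines the spending function and does not reconcile the α entered in it with the two comparisons. Under the literal reading with α = 0.05 at the interims and Holm at the end, the family-wise error is at its limit with one interim look and above it with two or more, reaching about 7.3% with five analyses. With 0.025 per comparison, the same literal reading stays within about 0.2 points of 0.05. The wrong definition alone therefore has a small effect, and the unstated α accounts for most of the excess.

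These figures rest on equally spaced looks, a correlation of 0.5 from equal arms, and no effect in either arm. The number and timing of looks are assumed. The conclusion is that the text as written does not secure the 0.05, not that the trial will exceed it.

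**What to change.** In section 9.5, define α₁(t*) as the cumulative one-sided error spent by t*, and state that every boundary, including the final one, is solved from the increments. Enter α = 0.025 in the function for each comparison, and state that once one comparison is rejected the other may use 0.05, as Holm allows. In section 9.1, state that the final Holm test uses the group-sequential final critical value. At the first step this is about 2.01 instead of 1.96 if there are four analyses.

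The cost is a change of wording in two sections. Power for each comparison falls from about 85% to about 84% with four analyses, and less with fewer. The sample size of 42 per group does not change. The α should be settled before any unmasked efficacy data are reviewed, because choosing it afterwards would weaken any claim based on an early stop.

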10. ETHICAL CONSIDERATIONS AND COMPLIANCE WITH GOOD CLINICAL PRACTICE

10.1. Statement of Compliance

This study will be conducted in compliance with the protocol and generally consistent with current Good Clinical Practices (GCP), adopting the principles of the Declaration of Helsinki, and all applicable regulatory requirements.

Prior to study initiation, the protocol and the informed consent documents will be reviewed and approved by an appropriate Independent Ethics Committee (IEC) or Institutional Review Board (IRB). Any amendments to the protocol or consent materials must also be approved before they are implemented.

10.2. Participating Centers

Participating TrialNet clinical sites must have an appropriate assurance, such as a Federal-wide Assurance (FWA), with the Office for Human Research Protections (OHRP), since they are actively engaged in research and provide informed consent. The protocol and consent forms will be approved by Institutional Review Boards at each of the participating clinical sites. HIPAA regulations will be followed by each participating institution in accordance with each institution's requirements. The participating international sites will obtain approval from their corresponding review boards in accordance with their local procedures and institutional requirements.

The investigator is required to keep accurate records to ensure the conduct of the study is fully documented. The investigator is required to ensure that all case report forms are legibly completed for every participant entered in the trial.

The investigational sites participating in this study will maintain the highest degree of confidentiality permitted for the clinical and research information obtained from participants participating in this study. Medical and research records should be maintained at each site in the strictest confidence. However, as a part of the quality assurance and legal responsibilities of an investigation, the investigational site must permit authorized representatives of the sponsor(s) and regulatory agencies to examine (and when required by applicable law, to copy) records for the purposes of quality assurance reviews, audits and evaluation of the study safety and progress. Unless required by the laws permitting copying of records, only the coded identity associated with documents or other participant data may be copied (obscuring any personally identifying information). Authorized representatives as noted above are bound to maintain the strict confidentiality of medical and research information that may be linked to identify individuals. The investigational site will normally be notified in advance of auditing visits.

